12.3 Planned Interim Analysis

No interim analysis is planned.

12.4 Final Analysis Plan

Primary Statistical Analysis:

Descriptive statistics will include frequencies (categorical variables) and means (continuous variables) of baseline covariates among the three intervention groups. Chi-square tests (for categorical variables) and t- or F-tests (via ANOVA for continuous variables) will be performed in a preliminary analysis to test for group differences.

For the primary outcome, we will use as an overall dental attendance score the number of years (over the two years of follow-up) in which the child visited the dentist. This will be an ordinal outcome with possible scores of 0, 1 or 2. To assess the intervention effect, we will use a generalized estimating equations (GEE) approach, with practices as clusters, based on a proportional odds marginal model. The model covariates will include an intervention indicator variable (equal to 1 for bundled intervention, 0 for enhanced usual care) and a set of baseline variables representing potential confounders. A standard error correction (for example, the method by Morel et al. 2003) will be used to adjust for a small number of clusters and 95% confidence intervals will be computed. This will be an intent-to treat analysis as all randomized participants providing the necessary measurements – regardless of any lack of compliance – will be included in the analysis.

In the event of missing data (for either year) for dental attendance, we will conduct sensitivity analyses by imputing responses under conservative assumptions (favoring the null hypothesis) and re-running the analysis described above on the completed data.

Analysis of Secondary Outcomes: Summary statistics (including means and standard errors) for secondary outcomes will be calculated by intervention group. The same approach as above will be used for binary or ordinal secondary outcomes (oral hygiene, frequency of sweet snacks and beverages). Namely, ordinal outcomes for each variable will be defined that summarize outcomes over time. For continuous outcomes (e.g., OH quality of life, cost), the above method

will be modified by using a linear model (identify link) for GEE, modeling the mean response over time as a summary measure. These outcomes will each be tested for normality using the Shapiro-Wilk statistic; outcomes for which normality is violated will be transformed where appropriate or an alternative model used. For count outcomes (e.g., dft accumulated over time), we will use a loglinear model (log link) assuming a negative binomial or other appropriate (e.g., zero-inflated negative binomial) distribution. For proportion outcomes (e.g., dt/dft), we will use GEE with a logit link, assuming the proportion follows a beta binomial or zero-inflated beta binomial distribution (Albert et al 2014). Similarly, we will fit appropriate GEE models to test for the effect of each implementation strategy on the corresponding outcome (e.g., % prescriptions given as a measure of adoption). As in the dental attendance analysis, the intervention indicator as well as pertinent baseline variables will be included in the model. In addition, interaction terms (baseline variables by intervention) will be included to test for possible effect modification.

For secondary analyses, a GLIMMIX model approach will be considered as an alternative, which may more easily allow for more than one cluster level if needed. Another alternative approach is to model the repeated measurements (again using GEE or GLIMMIX) which will add an additional cluster level – namely, for individuals). Goodness of fit of alternative models will be compared using QIC for GEE (or AIC for GLIMMIX).

In the likely event of missing responses, we will first assess (In the context of repeated measures analyses) whether the data are missing completely at random (MCAR), that is, whether missingness of the given outcome is dependent only on participant baseline characteristics and not further on the observed outcome at an earlier time. This will be done by modeling missing data indicators for the repeated measurements of each outcome using a GEE (or GLIMMIX) approach with a logit link and including appropriate baseline (control) variables and the outcome at the previous time if available. The MCAR null hypothesis will be rejected if the previous outcome has a statistically significant effect on the probability of missing. A nonsignificant effect would support the use of GEE (which assumes MCAR). The missing at random (MAR) assumption (that missing is not related to unobserved measurements), which is made in the GLIMMIX approach or under certain multiple imputation approaches, is not readily tested empirically, but will be evaluated via scientific/contextual considerations.

If the MCAR assumption is found to be violated we will use a multiple imputation (MI) approach in conjunction with the given GLIMMIX or GEE analysis using a suitable imputation model (i.e., using nonmissing outcome measurements as predictors of missing values). MI may also be considered if the MAR assumption is questioned for either GLIMMIX or GEE analyses.

In addition to assessing the overall effects of the interventions, we will investigate the mechanisms (or paths) through which interventions impact dental attendance. As represented in Figure 4.2.1, we hypothesize that significant portions of the intervention effect will occur through each of several paths. For example, intervention may affect provider variables (such as knowledge and self-efficacy) or practice variables (such as EMR documentation, practice readiness, climate, and attitude) which may in turn affect caregiver illness representation which may in turn affect child dental attendance. Alternatively, provider variables may affect child dental attendance via implementation outcomes. Summary measures may be used for some related mediators. For example, we will consider an overall average score for the multiple item scores for caregiver illness representation. We will also include and assess mediators that will

help reveal the importance of each of the multiple components of the bundled intervention. For example, we can estimate the proportion of intervention effect mediated by 'compliance' with regard to EMR documentation. A relatively high mediation proportion will suggest efficacy of the corresponding component.

We have previously developed a generalized causal mediation (GCM) analysis methodology and an accompanying R package (Albert & [name], 2011; Albert, Unpublished; Cho & Albert, Unpublished) which we will use to estimate and test each path effect and its proportion of the total intervention effect. The GCM method allows mediators and final outcomes of different types, including continuous, binary, and count (assumed to have normal, Bernoulli, and Poisson or negative binomial distributions, respectively). These options will accommodate the mediators and final outcome (dental attendance, summarized as a binary response) in our model. Each outcome (including mediators) is modeled using a generalized linear model that includes as covariates possible baseline confounders as well as causally preceding variables according to the causal model (as in Figure 4.2.1). The method uses an extended version of the mediation formula and assumes an extended version of the sequential ignorability assumption. (Albert et al., Unpublished) Bootstrap resampling is used to compute confidence intervals and a cluster bootstrap option is available to account for unexplained between-cluster (e.g. provider) variability.

Adjustment for Baseline Characteristics: Estimated intervention effects will be adjusted for the following baseline socio-demographic variables: child's age, race, and caregiver SES, education, and marital status.

Model Assumptions: We will assume that the probabilities of dental care receipt follow a logistic regression model with the included covariates and random effects. Per the standard approach, random effects will be assumed to be independent, normally distributed, and outcomes assumed conditionally independent given the random effects. If multiple random effects (e.g., for different cluster levels) are used, they will be assumed to be independent. For secondary outcomes, analogous assumptions, including the assumption of the correct link function, will be made.

Evaluations for the development of the Tool Kit: We will develop a tool kit containing the oral health didactic and skills curriculum, and resources (for providers and parents) that can be distributed to professional organizations (AAP, AAPD, ADA, AANP). This tool kit will be based on the results of the cRCT and will contain OH activities that have demonstrated to be effective, have content that is easy to tailor and apply for stakeholders beyond the study participants, and a table of contents for navigation to the relevant content. Specifically, the results of the cRCT (effectiveness of arm A vs. arm B), process outcomes from the cRCT (provider adoption, implementation metrics such as score cards of EMR audits and parent exit survey, costeffectiveness analysis) will be combined with the structured interview data that will be collected from the providers to evaluate the dissemination/diffusion strategy to be used for the tool kit. The newly developed OH tool kit would be reviewed by a random sample of 20% of participating primary care providers (\approx 12 providers) to obtain their views and input on whether the tool kit is easy to understand; use; provides the necessary information for the delivery of evidence-based oral health care in primary care settings; and to solicit any changes to be made.

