12.2 Sample Size Considerations

The study design will involve a cluster randomization to two arms:

1. Bundled (Practice + provider) interventions, 2. Enhanced usual care. The assumed response rates (proportion of children who have dental attendance) are Arm A: 0.46 (The dental utilization reported among Medicaid-enrolled children by Vujicic and Nasseh, 2015 was 48%, but we used 46% to be conservative), Arm B: 0.30 (based on pilot study where 30% of parent reported routine dental visit for child in the past year).

Eighteen practices (comprising the clusters) will be included in the study. Practices will be randomized to one of the two arms using a restricted randomization scheme with the constraint that 9 practices will be assigned to each arm. This approach will involve the computation of a balance score (for each candidate randomization) based on marginal differences in three key practice-level variables: % Medicaid-enrolled patients [20% to 40% and >40%], ratio of patients to providers, county [Cuyahoga vs. other]. We use the first generated (constrained) randomization that provides good balance according to a pre-selected balance criterion; it may be reasonable to require perfect marginal balance, if (as we expect) there are a reasonably large number of randomizations that yield this.

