The primary objective is to compare dental care attendance between the two arms. For simplicity in the power calculation we consider the binary outcome of any dental attendance in the two year period of follow-up. Dental attendance will be based on a single summary score (number of years - out of two - in which the child visits the dentist at least once a year). We thus suppose the use of a two-sided 0.05 alpha level z test (with pooled variance) for a difference in proportions. We assume, as a rough approximation, that the study will recruit an equal number of patients in each practice. Making conservative allowances for an intra-cluster (within-practice) correlation (ICC: in the binary dental attendance outcome) of 0.04 and a 25% drop-out rate, a sample size of 512 participants per arm (total n= 1024) will provide an estimated 80% power to detect the above difference in proportions. Alternatively, this sample size (actually 438 per group) will provide 90% power to detect this same effect size if the ICC is only 0.02. If the intervention effect is only 0.12 (0.42 versus 0.30), a sample size of 457 per group (914 total) will still provide 80% power with a dropout rate of 25% if the ICC is only 0.01. For the purposes of this study, a sample size of 512/arm (n=1024) will be recruited.

For sample size estimates, an important secondary outcome will be incidence of new decayed or filled teeth (dft). Mean dft is hypothesized to decrease for Arm A relative to Arm B. Our

previous data (Lee et al. 2015) among 5 to 7 year old low-income children suggests a mean dft for usual care of 4.5 (standard deviation = 7) which we assume to be a reasonable value for the enhanced usual care arm in the present study. We assume the same standard deviation for the new intervention group, assuming normally distributed responses for the power calculation. In fact, as dft is a count (possibly following a distribution such as Poisson or negative binomial) it is likely that the standard deviation will decrease with the mean, making our approach conservative (McCullagh and Nelder 1989).

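### Baseline differences between arms are tested without allowing for practice, so the p-values can overstate imbalance in this cluster trial

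*Combined protocol and SAP*

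**What the plan says.** Section 12.4 (Final Analysis Plan, Primary Statistical Analysis) opens with descriptive statistics of baseline covariates by arm. It then adds that chi-square tests for categorical variables, and t or ANOVA F tests for continuous ones, "will be performed in a preliminary analysis to test for group differences". No adjustment for practice is named there, and none is given for these tests elsewhere.

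The next paragraph describes the primary model, a proportional odds GEE with practices as clusters and a standard error correction for the small number of clusters. Its covariates are the intervention indicator and "a set of baseline variables representing potential confounders". Later in the same section, under Adjustment for Baseline Characteristics, five variables are named: the child's age and race, and the caregiver's SES, education and marital status.

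On the design, Section 12.2 says: "Eighteen practices (comprising the clusters) will be included in the study". They are allocated by restricted randomisation "with the constraint that 9 practices will be assigned to each arm", balancing on Medicaid share, patient-to-provider ratio and county. The sample size allows for an "intra-cluster (within-practice) correlation (ICC: in the binary dental attendance outcome) of 0.04 and a 25% drop-out rate", with ICCs of 0.02 and 0.01 as alternatives.

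**The concern.** The unit of randomisation is the practice. When a baseline characteristic varies between practices, the difference between arms has a larger variance than a chi-square or t test on individual children assumes. The test then rejects more often than its nominal level, even when allocation was sound.

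The plan recognises this in its sample size and in its primary model; only the baseline comparison leaves it out. Read at face value, a table of such p-values could lead readers to doubt the comparability of the arms for no good reason.

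**Working it through.** **Inputs**
- 18 practices, 9 per arm; 512 children per arm, 1,024 in total (Section 12.2).
- Children per practice at baseline: 1,024 / 18 = 56.9. Section 5.3 gives 56 to 57. Dropout does not apply at baseline.
- ICCs of 0.01, 0.02 and 0.04: the plan's values for the attendance outcome (Section 12.2).
- Assumption: baseline covariates have ICCs of that order. The documents give none, so 0.001 and 0.005 are added as a low range.

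**The plan's own figure first.** Section 12.2 uses a "two-sided 0.05 alpha level z test (with pooled variance) for a difference in proportions" with 0.46 against 0.30 and states that "a sample size of 512 participants per arm (total n= 1024) will provide an estimated 80% power".
- Without clustering, the pooled z test needs 144 per arm.
- With design effect 1 + (m − 1) × ICC, m = n / 9 and ICC 0.04, solving for n gives 144 × (1 − 0.04) / (1 − 144 × 0.04 / 9) = 138.24 / 0.36 = 384 analysed per arm.
- With 25% dropout, 384 / 0.75 = 512.

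The stated size reproduces, so the plan's own design effect can be applied to the baseline tests.

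**True error of a nominal 5% test that ignores practice**

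DE = 1 + (56.9 − 1) × ICC, and error = 2 × Φ(−1.96 / √DE).

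| ICC | DE | Chance of rejection |
|---|---|---|
| 0.001 | 1.06 | 5.6% |
| 0.005 | 1.28 | 8.3% |
| 0.01 | 1.56 | 11.6% |
| 0.02 | 2.12 | 17.8% |
| 0.04 | 3.24 | 27.6% |

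**Check by simulation.** This used 20,000 trials per setting, 18 practices of 57 children and simple allocation of 9 practices per arm. At ICC 0.01, 0.02 and 0.04, a binary covariate gave 11.7%, 17.4% and 27.7%, and a continuous covariate gave 11.8%, 18.4% and 27.6%. The formula holds.

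**Expected number of chance findings.** For the five covariates named under Adjustment for Baseline Characteristics, 5 × 0.116 = 0.6, 5 × 0.178 = 0.9 and 5 × 0.276 = 1.4, against 5 × 0.05 = 0.25 at the nominal level.

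**The case against.** The strongest reply is that little depends on these tests. They are preliminary, no decision rule uses them, and the primary analysis handles clustering properly. That is right, and it makes this a minor point.

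The size is also uncertain, for three reasons, all of which stand:
- The ICCs used are outcome ICCs. For a covariate that hardly clusters, the error stays near 5%.
- The formula assumes simple allocation of practices. The restricted randomisation would lower the rate for covariates tied to Medicaid share, patient-to-provider ratio or county.
- Practices differ widely in Medicaid share (Table 4.1.1 runs from 22% to 86%), which might be taken as proof that participants' characteristics cluster. Every enrolled child must be on Medicaid (Section 5.1), so that range describes the practices' whole panels and is only indirect evidence about participants.

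A reader might also infer that the primary model's covariates will be chosen from these p-values, because the open wording of the model follows directly after the tests. The documents do not support that: the section later names the covariates, and nothing selects them by significance.

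Finally, children are recruited after practices are randomised (Section 4), so a baseline difference could reflect differential recruitment and is worth examining. That is a fair reason to look at balance. It does not justify a test that cannot tell such a difference from ordinary variation between practices.

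**Conclusion.** The point holds as a minor one. As written, the baseline tests ignore the unit of randomisation and give p-values that are too small for covariates that cluster by practice. If covariate ICCs are like the plan's outcome ICCs of 0.01 to 0.04, with equal practice sizes and simple allocation, the chance of a false signal per variable is about 12% to 28% instead of 5%. At ICCs of 0.001 to 0.005 it is about 6% to 8%. That the tests ignore practice is read from the standard tests named and from the absence of any adjustment.

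Two stronger readings go too far. One is that every baseline test would reject far more often than 5%; that needs an ICC of about 0.01 or more for each covariate, which the documents do not establish. The other is that several variables will appear significantly unbalanced; for the five named covariates, the expected number is about one at the plan's ICCs.

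The primary GEE test is unaffected. The harm is limited to a baseline comparison that can mislead.

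**What to change.** In Section 12.4, delete the chi-square, t and F tests of baseline covariates. Report means or percentages and standardised differences by arm, with practice-level summaries if wanted. If tests are kept, state that they account for practice.

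In the primary-model paragraph, replace the open description of covariates with a reference to the list under Adjustment for Baseline Characteristics. Say there whether child medical illness belongs in that list, since Section 3.2.3 calls it a confounder and the list omits it. The same paragraph should speak of two intervention groups; it now says three.

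The cost is a wording change. Dropping the tests also reduces the analysis work. Design, data collection and sample size are unchanged.

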Précis: The study is a multi-site, multi-level, and multi-component cluster randomized clinical trial (RCT) to address poor dental utilization (attendance) and untreated caries among 3-6 year old Medicaid-enrolled children attending well-child visits (WCV) in primary care settings. The focus is on addressing factors (determinants) at the socio-ecological levels of the child's environment: provider (pediatrician and nurse practitioner), practice/organization level, and parent/caregiver level. Eighteen practices will be randomized to 2 arms: A) bundled multi-level intervention consisting of: 1. training medical providers in the Common-Sense Model of Self-Regulation theory-based education so that the provider delivers to the parent/caregiver the following: i) Core oral health facts about dental caries, and ii) prescription to visit the dentist and a list of dentists accepting Medicaid; 2. Integration of oral health assessments into EMR for the provider to document in the child's medical record; versus B) Control arm of medical providers receiving the American Academy of Pediatrics (AAP) based oral health education and providing usual AAP-based care for oral health. Each arm will consist of 9 practices. Children will be followed for 24 months or the completion of 3 consecutive WCV's to determine dental utilization and changes in oral health status.

[figure not shown]
Objectives:

Primary:
To examine the effectiveness of theory-based behavioral (provider level) and implementation (practice-level) bundled interventions versus enhanced usual care (AAP based oral health education) delivered by providers at WCVs in increasing dental attendance among 3-6 year old Medicaid-enrolled children.

Secondary:

- 1) Assess the effectiveness of interventions on secondary outcomes (e.g. development of new caries, changes in oral hygiene, oral health quality of life, frequency of sweet snacks and beverages, cost).
- 2) Assess potential mediators and moderators to investigate the pathways through which the multi-level interventions affect child primary and secondary outcomes.
- 3) Assess the adoption, reach, fidelity, and maintenance of providers and practices that affect child primary and secondary outcomes.

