2.2 Rationale

Ten million U.S. preschool and school-age children have untreated caries and profound disparities exist by race, socioeconomic status, and geographic region. Our studies in Cleveland have found that school dental screenings have not been effective in stimulating dental attendance ([name] et al., 2012) despite eligibility under the Affordable Care Act and coverage through Medicaid. Our pilot study results among 86 three to six year old Medicaid-enrolled children indicate that 36% (31 out of 86) had untreated dental caries (cavitation), much higher than the national average of 18% (Dye et al. 2017).

There are three core parent (or caregiver) issues: (1) awareness of importance of caries-free primary teeth; (2) understanding dental caries as a chronic disease that can be present even without symptomatic tooth pain; (3) navigating resources for dental care access. Thus, an accurate perception of dental caries is required for parental self-management strategies to take

care of their child's oral health needs. Also important is that parent/caregivers receive consistent OH facts from primary care settings, where young children are most often seen. In one study, two to five year old children were 3 times more likely to visit a dentist when advised by a primary health care provider, but this study also reported that low-income families were less likely to be advised (Beil & Rozier, 2010).

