3.2.2 Secondary Outcome Measures

Secondary outcomes will be assessed through clinical dental screenings for new primary and permanent decayed and filled teeth (dft/DFT: number of new cavitated lesions or restorations on teeth that were previously sound and number of new restorations on teeth that were previously decayed at the baseline WCV), questionnaire responses for oral hygiene (frequency of tooth brushing), diet (frequency of sweet food and drinks), and oral health-related quality of life (ECOHIS, numeric score) (Pahel et al., 2007). The direct and indirect dental costs will be assessed through various sources (See Table 8.1.2 for more details on cost elements and sources).

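### dt/dft, an example proportion outcome in Section 12.4, is undefined when dft is 0, so the planned GEE compares arms within a post-randomisation subset

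*Combined protocol and SAP*

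**What the plan says.** Section 12.4, under the analysis of secondary outcomes, covers proportions in one sentence: "For proportion outcomes (e.g., dt/dft), we will use GEE with a logit link". dt/dft is the only example. It is not among the secondary outcomes in Section 3.2.2, in Table 8.1.1 or in the child-level measures of Section 8.1.1. On the error distribution, that sentence of 12.4 ends: "assuming the proportion follows a beta binomial or zero-inflated beta binomial distribution".

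Section 3.2.2 builds dft from events after baseline: "number of new cavitated lesions or restorations on teeth that were previously sound and number of new restorations on teeth that were previously decayed". Earlier decay is judged against the first well-child visit. Section 12.4 gives the dft count its own model: "For count outcomes (e.g., dft accumulated over time), we will use a loglinear model (log link"), with negative binomial or zero-inflated negative binomial errors. Section 12.2 states the expected effect on it: "Mean dft is hypothesized to decrease for Arm A relative to Arm B".

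No section gives a value, a rule or an estimand for dt/dft when dft = 0. The missing-data text in 12.4 deals with responses that were not obtained, not with a ratio that does not exist. The intention-to-treat sentence concerns the primary analysis and reaches only participants who supply the measurements needed.

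**The concern.** The denominator of dt/dft is itself an outcome. A child with dft = 0 gives 0/0. In a binomial or beta-binomial likelihood, a child with no teeth at risk contributes nothing. Zero inflation does not help: it allows extra zeros in dt among children who have a denominator.

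The comparison is therefore conditional on dft above 0. If the intervention changes who has dft above 0, the two arms' subsets are no longer balanced by randomisation, and a difference in dt/dft may reflect who is in the set as well as how decay was managed.

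Under the Section 3.2.2 definition, membership depends on restorations too. A child whose baseline decay persists untreated, with nothing new, has dft = 0 and is left out. If that tooth is restored, the child enters with dt/dft = 0. Entry thus depends partly on dental attendance, the primary outcome. This matters because the Précis describes the trial as one "to address poor dental utilization (attendance) and untreated caries", and dt/dft is the only measure named in 12.4 that isolates untreated decay.

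**Working it through.** **Inputs.** From Section 12.2: Arm B has a "mean dft for usual care of 4.5 (standard deviation = 7"); Arm A mean 2.7; same SD; ICC 0.02; 25% dropout; 512 recruited per arm; stated power 74%. Nine practices per arm. The negative binomial is the plan's own candidate model for dft (12.4).

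**1. Reproduce the plan's dft power.**
- Retained per arm: 512 × 0.75 = 384; per practice 384/9 = 42.7.
- Design effect: 1 + (42.7 − 1) × 0.02 = 1.833; effective n = 384/1.833 = 209.5.
- z = 1.8 / (7 × √(2/209.5)) = 2.63; power = Φ(2.63 − 1.96) = 74.9%.

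This agrees with the stated 74%, so the inputs are read as intended.

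**2. Share of children with no ratio.** For a negative binomial, k = μ²/(σ² − μ) and P(dft = 0) = (k/(k + μ))^k.

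| Arm and assumption | k | P(dft = 0) | With a ratio, of 384 |
|---|---|---|---|
| B: mean 4.5, SD 7 | 20.25/44.5 = 0.455 | 34% | 254 |
| A: mean 2.7, same k | 0.455 | 41% | 225 |
| A: mean 2.7, SD 7 | 7.29/46.3 = 0.157 | 63% | 141 |

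The excess exclusion in Arm A is 41.4 − 33.7 = about 8 points, or 63.4 − 33.7 = about 30 points. Holding k implies an Arm A SD of √(2.7 + 7.29/0.455) = 4.3. Section 12.2 itself expects the SD to fall with the mean, so the lower end is more plausible.

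**3. Attendance also moves membership.** Assume 40% of children have a new lesion, independently 36% (31/86, Section 2.2) have baseline decay, and every child who attends has a decayed tooth restored. Then P(dft above 0) = 0.40 + 0.60 × 0.36 × attendance. With the 30% and 46% attendance of Section 12.2 this gives 46.5% and 50.0%. The 40% is assumed. Higher attendance enlarges the Arm A set, while prevention shrinks it.

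**4. Does the selection bias the ratio?** Illustrative simulation, 2,000,000 children per setting: gamma-distributed caries risk (k = 0.455), Poisson dft, and each child's chance of leaving a tooth untreated the same in both arms. Any arm difference in mean dt/dft then comes from selection alone.

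| Assumed link of untreated share to risk (logit per SD of log risk) | Arm B | Arm A, rate cut 40% for all | Arm A, lowest-risk 70% cleared |
|---|---|---|---|
| none | 0.500 | 0.500 | 0.500 |
| +0.6 | 0.574 | 0.583 | 0.636 |
| −0.6 | 0.426 | 0.416 | 0.364 |

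The shift is nil, about 0.01, or about 0.06, and its sign follows the assumed association. The last column is extreme: 70% of children have dft = 0 and mean dft is 3.6. With full weighting by teeth, the uniform cut gives no shift (0.633 in both arms for the +0.6 row).

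**5. A hand example, one assumed scenario.** Let 30% of each arm be high-risk affected children with ratio 0.6. Low-risk affected children, ratio 0.3, make up 20% of Arm B and 10% of Arm A. Mean ratio in B: (0.20 × 0.3 + 0.30 × 0.6)/0.50 = 0.48. In A: (0.10 × 0.3 + 0.30 × 0.6)/0.40 = 0.525. None of these shares or ratios comes from the documents. If high-risk children have 6 affected teeth and low-risk children 2, tooth weighting gives 1.20/2.2 = 0.545 and 1.14/2.0 = 0.570, about half the shift.

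**The case against.** The best defence is scope. dt/dft appears once, as an example. The caries outcome that the plan lists and powers is the dft count, which every screened child has; its model keeps caries-free children in. That stands: neither the primary outcome nor the dft comparison is touched.

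A second defence is that the plan never states an exclusion and may intend a rule, such as scoring dft = 0 as 0. That is possible. But it would be a different estimand, and the named distributions do not imply it.

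A third is that dt/dft asks a sensible question, namely whether existing disease gets treated, which a count of untreated teeth does not isolate. That also stands and is a real cost of the fix.

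Three stronger readings may tempt a reader; the documents support none of them.

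- **That up to 64% of children lack a ratio.** This takes the complement of the pilot's "36% (31 out of 86) had untreated dental caries (cavitation"). That figure is untreated decay at one time point, whereas dft accumulates and counts fillings. Under the new-events definition, baseline prevalence does not bound it at all.
- **That the analysis would make a preventive benefit look like harm.** This is one direction among several; steps 4 and 5 show that it rests on assumed associations. False benefit or no distortion is equally open.
- **That the analysed set is the children who developed caries.** It is not: a restored baseline lesion also brings a child in.

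**Conclusion.** The point holds as a defect in one example secondary analysis. Following 12.4 literally gives a comparison among children with dft above 0, a post-randomisation subset whose make-up the plan expects to change. On the plan's own dft figures, about 34% of Arm B and 41% to 63% of Arm A fall outside it, with the lower end more plausible.

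These shares rest on the negative binomial shape and on a mean of 4.5 taken from earlier data in 5 to 7 year olds. That mean may describe whole-mouth experience and not new events. If dft is whole-mouth, baseline caries already places many children in the set and the selection is weaker. The documents allow both readings, which is itself a reason to define the term.

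The bias cannot be sized or signed from the documents. It is nil if the tendency to have decay treated is unrelated to caries risk.

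**What to change.** Amend Section 12.4, and Section 3.2.2 to match:

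1. Define dt and dft for this purpose: new events since baseline, or whole mouth at the visit.
2. Make the randomised comparison of untreated decay on outcomes defined for every screened child: the untreated dt count (negative binomial GEE) and any untreated decay, yes or no (logistic GEE). Adjust both for baseline dt, with practices as clusters and the small-sample correction already planned for the primary analysis.
3. Report dt/dft by arm only as a description among children with dft above 0, with the number in that set and no between-arm test.

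The screenings at the three well-child visits should already supply the data, so the cost is wording. The downside is that untreated dt mixes new disease with treatment and so answers a slightly different question from dt/dft; the SAP should say so.
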